Participants' genetic information will be kept confidential to the extent possible. The results of participants' genetic testing will be kept in a locked and secured manner at the NIH. Genetic information will not be part of participants' medical record. Genetic information about participants will not be revealed to others, including their relatives, without participants' written permission. Similarly, participants will not receive information about other family members.

Problems, such as with insurance or employment discrimination, may occur if participants disclose information about themselves or agree to have their research records released. We will not release any information about participants or their families to any physician, insurance company or employer unless you sign a document allowing release of the information.

Further discussion can be found under Section "20. Confidentiality" on pages 51-52.

7.o. Accelerometry: The accelerometer has no risks associated with its use and causes minimal inconvenience.

7.p. 5-2 CR/Control Diet: Overall, a minority of participants (9-15%) is expected to develop minor physical and psychological AEs during the first several weeks of 5-2 CR. Such AEs include lethargy, feeling cold, difficulty concentrating, and irritability. Participants may experience minor psychological symptoms such as feeling hungry (leading to preoccupation with food), lack of concentration, bad temper and irritability. The Harvie et al. study is especially important because our study design is similar to it. In the Harvie et al. study, a small number of participants on the 5-2 CR regimen (8%) reported physical symptoms including lack of energy, headaches, feeling cold, and constipation. Minor psychological symptoms included lack of concentration, bad temper, and a preoccupation with food among 15% of the 5-2 CR group. These adverse effects abated after cessation of CR. Conversely, 6% of 5-2 CR participants reported better health and increased energy.⁴⁰ Furthermore, 32% of 5-2 CR had increased self-confidence and positive mood. To minimize these risks, participants will be told ahead of time about potential side effects. During Compliance Visits, we will give participants the opportunity to discuss and will offer encouragement that may ameliorate minor psychological symptoms.

No major adverse effects have been associated with mild to moderate intermittent calorie restriction.^{39,40,94} Two of our previous CR studies did not have a reported serious AE incident.^{39,40} More severe caloric restriction in humans relative to our studies also produced no serious AEs⁹⁴. We classify the 5-2 CR and control diet as minimal risk.

8. Subject safety monitoring

8.a. Monitoring of Subjects

The investigator or clinical staff performing a study procedure will monitor subject safety. This includes physicians, licensed practitioners (NPs) and RNs during LPs, blood draws, mixed meal testing, and History and Physical sessions; investigators administering questionnaires and cognitive testing, MRI techs and investigators during MRIs.

The PI will make determinations regarding the presence and grading of on adverse events (AEs) and unanticipated problems (UPs). Whenever study investigators contact subjects throughout the study, they will seek information on AEs and UPs. AE's and UPs will also be elicited during study visits, by subjects filling in the symptoms review questionnaire or during history and physical examination. Participants will be asked to use electronic mail (Secure Email & File Transfer Service: <https://secureemail.nih.gov/bds/Login.do>) or telephone to inform the investigators about any AE's or UPs experienced. AEs and UPs may be observed by the Investigator and/or study staff, elicited from the subject and/or family member, or volunteered by the study subject. AEs and UP's that had previously been reported by study subject will also be reassessed for duration, intensity and

possible reoccurrence. Assessment of safety will include vital signs, history and physical sessions, questionnaires on physical and psychological symptoms and clinical labs as indicated. Any AE or UP that occurs between the times a study participant signs the informed consent form and the end of participation will be assessed and recorded under NIH HRPP SOP # 16 and 16 A.

In particular, we will monitor the weight loss of the participant. If a participant on 5-2 CR loses 4-5% of their body weight within a 2-week period between visits, additional safety visits will be scheduled every week to monitor body weight more closely. If weight loss in that range or greater continues to occur, participants will be removed from the study.

A study participant will also be discontinued from the study if:

- Any adverse event occurs Grade 2 or greater and possibly related to the study.
- The participant develops any of the exclusion criteria.
- There is persistent non-compliance with study requirements (keeping follow-up visits).

Participants will be informed about new information from this or other studies that may affect their health, welfare, or willingness to stay in this study. Participants may decide to stop participating at any time. Any data or blood collected until that point in time will remain part of the study and are the property of the National Institute on Aging.

9. Outcome measures

All secondary outcome variables in this pilot study are exploratory.

9. a. Primary outcome measures

- Exosomal p-S312-IRS-1/p-panY-IRS-1 ratio

9. b. Secondary outcome measures

- Other exosomal protein and mRNA biomarkers of AD;
- S_I and HOMA-IR, indices of insulin resistance, derived from insulin and glucose values taken from a fasting blood draw;
- fMRI activation to appetitive food versus non-appetitive food stimuli;
- Resting state fMRI intrinsic functional connectivity of DMN;
- Behavioral performance and fMRI activation during a Color-Word Stroop task;
- Brain metabolites assessed with Magnetic Resonance spectroscopy and regional perfusion assessed with arterial spin labeling;
- Memory and executive function scores.
- Anthropometric measures (weight, waist circumference, sagittal diameter);

- Clinical Labs: lipid panel, uric acid;
- Plasma ketones, such as β -hydroxybutyrate and other metabolites.
- Plasma metabolites and hormones (GLP-1, insulin) during a mixed meal test;
- CSF and plasma AD biomarkers, including $\text{A}\beta_{1-42}$ and p_{181}Tau ;
- Plasma and CSF neurotrophic factors, such as BDNF;
- Plasma and CSF reactive oxygen species, advanced glycation end-products and advanced oxidation protein products;
- Plasma and CSF pro-inflammatory cytokines, such as IL-6, IL-8, IL-12 and IL-23;
- Ratings of symptoms that can occur with 5-2 CR, mood and quality of life changes, recorded during both the 5-2 CR and control diet phases;
- Physical activity measured using an accelerometer.
- Global gene expression pattern, mitochondria gene expression and expression of other gene pathways responding to CR
- Genome-wide methylation in peripheral blood mononuclear cells

10. Statistical Analysis

10. a. Analysis of data/study outcomes

This is a pilot study that is exploratory in nature and one of its goals is to collect preliminary data for multiple outcomes that may be used in future studies on the brain effects of CR.

For the primary and each secondary scalar measure, a separate repeated measures mixed models analysis will be conducted to examine the effects of the between-subjects factor “Group” (5-2 CR group vs. “Healthy living” control group), the within-subjects factor “Time” (Baseline vs. Outcome) and their Interaction. An Auto-Regressive (AR)1 covariance matrix and Restricted Maximum Likelihood Estimation (REML) will be used. We will assess fit to the model using the AIC and BIC criteria (lower values indicate better fit). These parameters were chosen because they are recommended for repeated measures analyses, including fMRI task analyses.¹⁰⁰ Regarding within-subjects effects, we will assess post-hoc differences between the 8-week outcome visit and baseline for the 5-2 CR and control groups and for each group separately (i.e. post-hoc tests for the Group * Time interaction). This analytic approach is common in the CR literature.¹⁰¹ Mixed model post-hoc tests will employ the Least Significant Difference (LSD) statistic. We will use one-tailed t-tests.

Criteria for significance will be set at alpha of 0.05 for all non-MRI analyses, and 0.005 uncorrected at the voxel level for fMRI analyses. Given that this pilot study is exploratory, we will not conduct correction of multiple comparisons for the various secondary outcomes.

Analysis of fMRI data will use a mixed model design to assess the effect of Group on

brain activation associated with viewing appetitive vs. non-appetitive food, the Stroop effect in the Stroop task, and DMN intrinsic functional connectivity. Analyses will be conducted at the whole brain level and within ROIs (vmPFC, OFC and insula for the fMRI food task, lateral and dmPFC for the Stroop task, and in DMN for resting state. The fMRI analyses will be corrected for type 1 error as the cluster level using Monte Carlo simulations.

For brain MRS measures, a repeated measures analysis will be separately used for each of the brain regions of interest: the hippocampus and the prefrontal cortex.

APOE genotype is a common covariate used when assessing populations with AD or at risk for AD. We intend to perform exploratory analyses including APOE, which may reduce error variance and improve our statistical models.

Plasma ketones are strongly affected by alternate day CR acutely but not chronically;³⁹ our main objective for measuring them is to assess compliance with 5-2 CR.

We do not anticipate a change in physical activity in 5-2 CR versus “healthy living” control groups, because no change has been noted in our previous studies. Nonetheless, this is a common analysis requested by reviewers, to make sure that exercise effects did not contaminate diet effects.

The data from the gene array and DNA methylation array will be analyzed using residuals after adjustment for white blood cell differential count in linear regression models. We will take two approaches to analyze the data. First we will focus on candidate genes approach where we select specific expression probe or CpG sites; DNA for these studies will be collected during Baseline, Compliance and Outcome Visits. Second, we will run genome-wide association analysis for differences in cross sectional and longitudinal changes in gene expression or DNA methylation between the control and 5-2 CR group at each gene array probe or CpG site. DNA for genome-wide association analyses will only be collected during Baseline and Outcome Visits. For the cross sectional analyses, we will use a paired t-test at each visit, and mixed models for longitudinal analysis. In addition, we will look at overall patterns of gene expression and methylation using principle components, DIANE and hierarchical clustering tools to determine whether there are specific gene expression and methylation signature in association with 5-2 CR. As secondary analyses, we will also determine whether gene expression and DNA methylation patterns can predict the changes in metabolic, cognitive and neurochemical variables collected in this study. Within the 5-2 CR group, we will test the association between baseline levels of gene expression or DNA methylations at each probe/CpG site with longitudinal changes in the main outcome variables using mixed models.

10. b. Power analysis

The accrual number request is 100 participants. Our target sample size for completing the study is $N = 40$. There will be 20 participants in each group. We anticipate up to 60 participants will not meet inclusion criteria during the screening visit or may withdraw from the study. Enrollment will continue and withdrawals will be replaced until we have acquired complete data from 40 participants.

For power calculations, we used G*Power (<http://www.gpower.hhu.de/en.html>).

First, we calculated power for the primary outcome (exosomal p-S312-IRS-1/p-panY-IRS-1 ratio, which is a measure of brain IR). Effect size (f) was determined based on studies with comparable sample sizes examining moderate CR (20-40%) over a 2-3 month period in humans.

Insulin Sensitivity (Peripheral and Brain): It is important to re-emphasize that reductions in fat mass will increase peripheral insulin sensitivity.^{12,21,22} To determine effect size, we examined a study by Weiss and colleagues¹⁰¹ that had a design similar to our own. They examined sedentary men and women aged 50-60 with a BMI of 23.5 to 29.9. They randomly assigned participants to moderate CR ($n = 18$) or a healthy lifestyle control group ($n = 10$) for 12 months. The CR group showed a significantly reduced BMI from 27.1 to 24.8, with a corresponding increase in S_i from 4.5 to 7.4. The healthy living control group showed a non-significantly reduced BMI from 27.9 to 27.4, with a non-significant increase in S_i from 4.2 to 4.5. The effect size was $f = 0.440$. Our most recent study on intermittent CR⁴⁰ showed a reduction of body fat from 33.6kg to 30.6kg by 3 mo., but a relatively smaller decrease (29.1kg) by 6 mo., suggesting that most of the weight loss occurred in the first three months. Based on these findings, we anticipate a comparable effect size (0.3) from our 8 weeks of 5-2 CR.

Regarding our primary outcome (exosomal p-Ser312-IRS-1/p-panY-IRS-1), in our published study, we examined differences between preclinical samples from participants who eventually developed AD (92.1 ± 7.7) and controls (14.7 ± 0.9)⁵¹. We base our power analysis on the assumptions that the our subjects at high risk for AD had intermediate high values for p-Ser312-IRS-1/p-panY-IRS-1 ratio at baseline (ratio = 46), that the 5-2 CR intervention had a similar modest effect size as for peripheral IR in decreasing the ratio (0.3), whereas the control intervention induced no change. We used the following input parameters to determine power for ANOVA repeated measures, between-within interactions: $\alpha = .05$ (one tailed); 2 groups (5-2 CR vs. Healthy Living diet); 2 repeated measures (Baseline vs. Outcome); correlation between repeated measures = 0.4. Based on these parameters, we achieve over 90% power with a total 40 participants (see Figure 4 below for post-hoc power calculation (achieved power, given certain N and effect size)). These calculations are conservative (e.g. the effect size may be greater than 0.3); therefore, it is likely that we will actually achieve greater power in this study.

[figure not shown]

Figure 4. Post-hoc power calculation for primary outcome (exosomal p-Ser312-IRS-1/p-panY-IRS-1) analyzed with ANOVA for repeated-measures for within-between interaction. The x-axis depicts total sample size and the y-axis depicts Power.

In addition, we performed power calculations for several key secondary outcomes of interest.

Regarding fMRI, we performed power calculations based on a series of equations by Mumford and Nichols¹⁰⁰ that take into account the unique nature of fMRI data. We use an alpha = .005 for fMRI analyses, as recommended by Mumford and Nichols.

fMRI task 1 (appetitive foods): A recent study by Bruce et al.¹⁰² examined young to middle-aged obese participants that either underwent 3 mo. of moderate CR (n=16) or bariatric surgery (n=15). They assessed fMRI activation to pictures of food versus pictures of animals at baseline and 3 mo. They found that CR participants showed a large cluster-wide increase in medial prefrontal cortex versus bariatric participants ($t = 3.72$, Cohen's $d = 1.34$ and $f = 0.8$), a brain region that they argue is involved in regulating appetite and suppressing cravings. To achieve at least 80% power with 20 subjects per group in a between subjects contrast, we would require a scan time of 6 min. for the fMRI task. Our scan time of 24 min. well exceeds this estimate and would achieve power of roughly 85-90%.

fMRI task 3 (resting state fMRI): Zhang et al.¹⁰³ recently published a proof-of-concept study on the acute effect of intranasal insulin (40 IU) on 14 subjects with type 2 diabetes and 14 healthy participants. Intranasal insulin, like CR, increases insulin availability in the brain.¹⁰⁴ They in part examined changes in resting state fMRI brain activity during placebo (day 1) and intranasal insulin (day 2 or 3), collapsed across groups. They found

robust activation in several brain networks, including a portion of DMN in a medial PFC area ($t = 3.25$, Cohen's $d = 1.25$ and $f = 0.626$) similar to what is described above for Bruce et al.¹⁰² To the best of our knowledge, this is the only published study examining the effect of a therapeutic intervention manipulating brain insulin on resting state activity. We anticipate a similar activation pattern and effect size in our data. According to calculations based on Mumford and Nichols¹⁰⁰ for power estimation in fMRI, groups with $n=20$ each would require a 6-minute resting state scan to achieve 80% power. Our resting state scan lasts for approximately 7.5 minutes.

Memory and Executive Function: Witte and colleagues⁶⁵ examined aged participants divided into groups that either engaged in 3 months of moderate (30%) CR ($n=20$), received no intervention ($n=10$), or received unsaturated fatty acid supplementation ($n=20$). For the Rey Auditory Verbal Learning Test, which is very similar to our CVLT, CR participants showed a significant 130% gain (Cohen's $d = 0.799$) in a composite memory score after the intervention versus non-significant changes in the other groups. Our own intervention only differs in the length of time spent on CR and the intermittent nature of the CR, and so we anticipate a comparable effect size. Given that executive function is more consistently impacted by obesity and by extension IR across the lifespan,^{105,106} we also anticipate a similar or greater effect size for executive function, although there are currently no studies in the literature directly comparable to our design. In summary, with an anticipated effect size $f = 0.4$, we will have power = 0.81 to detect an effect on cognition.

Plasma biomarkers: For plasma biomarkers, such as proinflammatory cytokines, ROS, BDNF, and affect measures, we note that our previous within-subjects study on intermittent CR in humans³⁹ produced robust differences in significant or near-significant trends in these measures by 3 mo. with $n = 42$ at alpha = .05. We anticipate being able to detect such effects and more subtle differences, because our between-subjects design is more powerful. In particular, informal power calculations suggest that we will have at least 80% power to detect differences in cytokines, ROS, and BDNF.

Global gene expression and genome-wide methylation: With sample size of 20 for each of the two groups, using the Illumina HT12 expression chip with 25,000 annotated genes, there is 80% power at alpha (two-tailed) = 0.05 to detect a 1.5-fold difference in expression. Similarly, with the sample size of the proposed study, we have 90% power to detect methylation differences of 40% between groups at alpha (two-tailed) = 0.05 for 45,000 CpG sites.

11. Human subjects protection

11. a. Subject selection

Statement of equitability

Participants will be recruited and enrolled equitably including, but not limited to,

without regard to race, ethnicity, sex, sexual orientation, unless explained below.

It is National Institute on Aging (NIA) policy that the regulations of the Department of Health and Human Services (HHS), set forth in 45 CFR Part 46, are applicable to all research involving human subjects, as defined by these regulations, for which the NIA is responsible, regardless of the source of funding or whether the research is funded. In the case of conflict between regulations of the funding or regulatory agency and HHS, the more restrictive regulations shall prevail. The NIA is also obligated by law to adhere to the regulations of the Food and Drug Administration (21 CFR Parts 50 and 56) governing projects involving investigational new drugs [within the meaning of 21 U.S.C. sections 355(i) or 357(d)], or investigational new devices [within the meaning of 21 U.S.C. section 360(g)].

Rationale for non-equitable selection

This study imposes certain age and BMI limits to define a suitable population of older overweight adults with IR, which is suitable for addressing the study hypotheses, as explained in the introduction. The main reason we study participants aged 55-70 years who are overweight and have IR is to examine brain IR and other AD-associated biomarkers at individuals at higher risk for disease during the preclinical stage of AD. We impose a lower limit of BMI to ensure that we will recruit a population with high probability of IR. IR is present in many middle-aged²³ and aged^{24,25} adults with a BMI above 27.²⁶ Specifically, higher visceral adiposity due to being overweight or obese corresponds to higher IR in 25-40% of late middle-aged to geriatric Caucasian⁴² and Asian²⁷ populations. Overweight to obese participants (BMI ≥ 27) aged 55-70 years have insulin sensitivity values of approximately $7.6 \text{ min}^{-1}/(\mu\text{U mL}^{-1}) \times 10^{-4}$.^{24,25} In addition, we impose the upper limit of 350 pounds for body weight, because this is the limit of the scanner. In addition, we exclude pregnant women, given the fact that we employ brain MRI and Xrays for fluoroscopy-guided LPs, which may pose a higher risk to the unborn fetus. We exclude nursing women because they have higher caloric needs.

11. b. Justification for exclusion of children

The goal of this study is to provide proof of concept that 5-2 CR compared to dietary counseling can lower IR and ameliorate any detrimental effects on middle to older age cognitive performance, brain metabolism and function and normalize any biomarker abnormalities associated with higher risk of AD. Children do not develop AD, and there are no data to suggest that IR during childhood may impact future AD risk. In addition, 5-2 CR in juvenile animals permanently stunts their physical growth. Children are, therefore, not an appropriate population to examine for the purposes of our study.

11. c. Justification for exclusion of other vulnerable participants

If the present study provides proof of concept that 5-2 CR compared to dietary

counseling improves cognitive performance, brain metabolism and function and normalizes biomarker abnormalities associated with higher risk of AD, it would “pave the way” for testing it in cohorts with age-related cognitive impairment or AD. The study requires following strict instructions for 5-2 CR diet, which participants with cognitive impairment would find hard to follow. In addition, this is a proof of concept study that involves more than minimal risk without direct benefit. The study involves some minor but real discomfort (e.g. feeling hungry) and invasive procedures (such as LP), which are not appropriate for those without consent capacity in this study.

11. d. Justification of sensitive procedures

The experimental paradigm does not involve the use of deception, or other sensitive procedures.

11. e. Safeguards for vulnerable populations

We will perform pregnancy tests and exclude pregnant (and nursing) women.

11. f. Qualifications of investigators

The Principal Investigator has verified that all individuals working on this protocol required to take HRPP training under OHSRP SOP 25 (Training requirements for the NIH Human Research Protections Program) have completed all required training.

[name]. (LCI/NIA)

[name] is a Board-certified neurologist with subspecialty training on dementia and Experimental Therapeutics in Neurology. He will be principal investigator and medically responsible investigator of the protocol. He has been primarily responsible for the design of the study and will oversee the project, ensure quality assurance of the data and analyze the data. He will obtain consent, conduct History and Physicals and perform LPs.

[name]. (LNS/NIA)

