PRECIS

Being overweight or obese can cause insulin resistance (IR), which is defined as reduced responsiveness to insulin by the cells of various tissues or organs. IR at midlife increases the risk of developing Alzheimer's disease (AD). We recently discovered novel biomarkers of brain IR (altered Tyr and Ser phosphorylated forms of insulin receptor substrate 1; IRS-1) in plasma exosomes enriched for neuronal origin. Moreover, IR is associated with AD biomarkers including deficits in resting state brain activity and cognitive performance. Calorie restriction is defined as consuming fewer calories than what is considered normal without a lack of nutrients. A certain type of calorie restriction, in which one consumes 500-600 calories a day for two consecutive days, followed by non-restricted eating for 5 days (5-2 CR), has been shown to lower peripheral insulin resistance effectively. Effects of CR and lowering peripheral IR on brain IR and cognition are unknown. The goal of this exploratory pilot study is to provide proof-of-concept that 5-2 CR at midlife can reverse brain IR, lower peripheral IR, improve cognitive performance, and increase brain activation at rest and during tasks. Specifically, we will study the effects of 8 weeks of 5-2 CR versus a control dietary intervention on brain and peripheral IR, memory and executive function, resting state default mode network activity, brain metabolism, and AD biomarkers. Forty overweight to obese women and men (between 55 and 70 years of age) will be randomized 1:1 into 5-2 CR and control groups. In the 5-2 CR group, participants will be offered "healthy living" dietary counseling at baseline, which they will be instructed to implement for five days/week. For each of the other two consecutive days/week, they will consume two shakes (Boost®, CWI Medical), providing a total of 480 Kcal/day. In the control group, participants will be offered "healthy living" dietary counseling at baseline, which they will be asked to implement for every day of the week. Participants will undergo screening including a history and physical examination, calculation of Body Mass Index (BMI, which must be ≥ 27) and a blood draw for insulin and glucose to determine whether they have insulin resistance. If participants meet eligibility criteria, they will continue with a baseline visit involving anthropometric measures, questionnaires, tests of cognitive function, brain MRI, blood draws for plasma and peripheral blood mononuclear cells, and lumbar puncture for cerebrospinal fluid biomarkers of AD. After 8 weeks, we will collect the same measures. To assess and reinforce compliance with their respective diet, participants will come into the clinic every 2 weeks to discuss compliance, measure their body weight and perform blood draws for measurement of ketones to objectively confirm energy restriction for the 5-2 CR group. We will also contact participants every week to further ensure compliance. To assess the effects of the diets on physical activity, participants will be asked to wear an accelerometer for 96 hours before and after they are on the diet.

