Finally, we will measure proteins and RNAs implicated in AD pathogenesis and insulin signaling in neuronal-origin plasma exosomes. These include, but are not limited to A β ₁₋₄₂, total tau, p₁₈₁Tau, p-S396-Tau, p-S312-IRS-1, p-panY-IRS-1, cathepsin-D, ubiquitin, LAMP2, HSP70, and CD81.⁸¹

Physical activity: To assess baseline activity-associated variance in other outcomes, as well as the effects of the two diets on physical activity, we will use accelerometry. We hypothesize that the 5-2 CR group will not show any differences in physical activity

compared to baseline and the control group. Nonetheless, this analysis is expected in many manuscripts on dietary interventions, in order to rule out effects attributed to differences in physical activity.

Gene expression: To understand the molecular mechanisms of the benefits of calorie restriction, several studies have utilized gene expression changes using microarray in mammals. In a recent meta-analysis of publically available CR microarray data from mouse, rat and pigs in gene expression changes were analyzed across various tissues including liver, kidney, heart, mammary glands, muscle, lung, brain, and adipose.⁸² There were 174 genes that were significantly over- or under-expressed, some of which were tissue-specific but others were found in more than 3 tissue types. The functional categories that were enriched included genes involved in growth hormone signaling, lipid metabolism, immune response, retinol metabolism, copper ion detoxification, and circadian rhythms. These results highlighted the complex patterns of changes that occur with CR that span across many domains.

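### The accelerometry analysis is asked to exclude physical activity as an explanation of the diet effects, but the plan's only criterion is a superiority test with 20 per arm, and a non-significant result cannot support that conclusion

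*Combined protocol and SAP*

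**What the plan says.** Section 1 (Physical activity) hypothesises that activity in the 5-2 CR group will differ neither from its own baseline nor from control, and adds that "this analysis is expected in many manuscripts on dietary interventions, in order to rule out effects attributed to differences in physical activity". Section 10.a again expects no change and says that the analysis is done "to make sure that exercise effects did not contaminate diet effects".

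Activity is a secondary outcome in section 9.b ("Physical activity measured using an accelerometer"), and section 9 calls all secondary outcomes exploratory. The analysis comes from the general rule in section 10.a: "For the primary and each secondary scalar measure, a separate repeated measures mixed models analysis will be conducted", with Group, Time and their interaction. On the decision rule, the same section says "Criteria for significance will be set at alpha of 0.05 for all non-MRI analyses" and "We will use one-tailed t-tests".

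The PRECIS says that participants "will be randomized 1:1 into 5-2 CR and control groups", and section 10.b says "There will be 20 participants in each group". Sections 10.a and 10.b contain no margin, no confidence-interval criterion, no activity-adjusted model and no power figure for activity. Section 4.d.1 places the two 96-hour recordings between the screening and baseline visits and after the Week 8 Outcome Visit.

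**The concern.** The stated purpose is a negative conclusion: activity did not differ, so exercise does not explain the results. The planned tool is a test built to detect a difference. If that test is non-significant, it says only that a difference was not shown. In a trial of this size a relevant difference could easily remain compatible with the data.

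The one-tailed rule adds a second difficulty. A hypothesis of no difference has no favoured direction, the plan names none for activity, and a one-tailed test cannot flag a difference in the untested direction.

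At stake is the interpretation of the brain insulin resistance, peripheral insulin sensitivity and cognition results. Section 1 itself lists lack of exercise among the factors associated with higher insulin resistance. A report that activity had been excluded as an explanation would claim more than the analysis can show.

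**Working it through.** **Inputs from the documents.** 20 per arm and alpha 0.05, one-tailed (sections 10.a and 10.b). Withdrawals are replaced until 40 participants have complete data (10.b), so no dropout allowance is made. The correlation of 0.4 between repeated measures is the value section 10.b uses for the primary outcome.

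**Assumptions.** The documents give no SD, relevant difference or correlation for activity. I take a true between-arm difference in change of 0.5 SD of the raw measure as a benchmark, and correlations r of 0.4 (borrowed from the primary outcome), 0.6 and 0.8.

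**The plan's own power figure.** Section 10.b states over 90% power for the primary outcome with f = 0.3, r = 0.4, N = 40 and two measurements.
- Noncentrality = f² × N × m / (1 − r) = 0.09 × 40 × 2 / 0.6 = 12, with 1 and 38 degrees of freedom.
- Power = 92.2% for the F test at 0.05, or 96.1% for the one-tailed equivalent.

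The stated figure reproduces. There is no corresponding figure for activity.

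**Chance of missing a 0.5-SD difference.** With two visits and complete data, the Group by Time test is a two-sample t-test on change scores.
- SD of change = SD × √(2(1 − r)).
- Noncentrality = (0.5 / √(2(1 − r))) × √(20/2), with 38 degrees of freedom.
- 95% CI half-width = 2.024 × √(2/20) × √(2(1 − r)) = 0.640 × √(2(1 − r)), in SD units and with the SD at its assumed value.
- The difference detectable with 80% power is 0.909 SD of change (two-sided), multiplied by √(2(1 − r)).

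| r | SD of change | Noncentrality | Missed, two-sided | Missed, one-sided (correct direction) | Detectable at 80%, two-sided | 95% CI half-width |
|---|---|---|---|---|---|---|
| 0.4 | 1.095 | 1.44 | 71% | 59% | 1.00 SD | 0.70 SD |
| 0.6 | 0.894 | 1.77 | 59% | 46% | 0.81 SD | 0.57 SD |
| 0.8 | 0.632 | 2.50 | 32% | 21% | 0.57 SD | 0.40 SD |

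At r = 0.4 or 0.6, even an observed difference of exactly zero would typically leave 0.5 SD inside the 95% interval. At r = 0.8 it would not, but an observed difference of little more than 0.1 SD would bring 0.5 SD back in (0.10 + 0.40 = 0.50).

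**Would a formal equivalence rule help?** With a margin of 0.5 SD and no true difference, the 90% CI falls wholly inside the margin in about 1% (r = 0.4), 10% (r = 0.6) or 58% (r = 0.8) of simulated trials. Except at high correlation, the design can rarely deliver the negative conclusion.

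**The case against.** The best defence has four parts.

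- **The rule is not written.** A reader might infer that the plan declares activity equal whenever p exceeds 0.05. No section says so. The mixed model yields an estimate and a standard error, and nothing prevents an interval from being reported. This stands: the rule is implied. But no other criterion is offered for a conclusion that the plan states twice.
- **The miss rates are conditional.** A reader might also infer that the test misses a 0.5-SD difference most of the time. That is true at r = 0.4. At r = 0.6 it is true only two-sided, and at r = 0.8 it is false. The 0.5 SD is a chosen benchmark, and 0.4 belongs to another outcome. This stands too, so the figures are an illustration. The logical point needs none of them.
- **The plan does more than the between-arm test.** Section 10.a adds post-hoc comparisons with baseline in each arm, and section 1 also mentions variance in other outcomes linked to baseline activity. The within-arm comparisons are again tests for a difference, and section 10 specifies no model for the second purpose. Neither supplies a criterion for absence of a difference.
- **The consequence is limited.** The outcome is secondary and exploratory. A difference in activity that arises after randomisation bears on how the diet works, not on whether the randomised comparison is valid. This stands and limits the severity. Exploratory status excuses low power, but it does not support a firm negative statement.

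**Conclusion.** The concern holds in a limited form. The stated purpose of the activity analysis goes beyond what a superiority test with 20 per arm can support, and the one-tailed rule has no defined direction for this outcome. The size depends on the assumed 0.5-SD difference and on the correlation: two-sided miss rates run from 71% down to 32%, and 95% CI half-widths from 0.70 to 0.40 SD, as r goes from 0.4 to 0.8.

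The timing of the recordings sets a further limit. They bracket the eight weeks, so activity during the diet period is not directly measured. Even a narrow interval could not exclude a difference in that period.

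The documents do not support the inference that the primary comparison is compromised. This is a minor-to-moderate point about what the report may say in explaining the effects.

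**What to change.** - **Section 10.a, analysis.** For physical activity, report the between-arm difference in change with a two-sided 95% confidence interval in place of the one-tailed test. State that a non-significant result will not be read as showing equal activity.
- **Sections 1 and 10.a, purpose.** Change the language about ruling out activity effects, and about making sure that exercise did not contaminate the diet effects, to describing or assessing activity.
- **Limitation.** State that recordings are made before baseline and after the Week 8 visit, so activity during the diet period is not directly measured.
- **Optional margin.** An equivalence margin, chosen by the sponsor and fixed before analysis, is needed only if a claim of no relevant difference is still wanted. That claim should be limited to the recorded periods.

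The cost is wording only, with no added participants, visits or data. The downside is that the report will probably have to say that a contribution of activity could not be excluded.
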